6.5. Visit Windows

Visit windows will be assigned based on the analysis need and the type of data. There are two types of data to be assigned an analysis visit: diary data and non-diary data.

Visit Windowing for Diary Data:

For diary data (micturitions, UUI, urgency episodes, total incontinence etc.), where the assessment has been performed at a specific visit (for example confirmation of completion of diary) the assessment will be analyzed at the scheduled visit entered. For diary data whereby only a date/time is given, the record will be assigned based on the dates of the scheduled visits performed. For example, if Run-in visit occurs on 01SEP2018 and Baseline visit occurs on 14SEP2018, any diary data occurring after 01SEP2018 up to and including the day before Baseline visit (13SEP2018) will be windowed for the analysis as “Baseline”. This applies for all analysis visits except for Week 2 and Week 4 as there is no Week 2 scheduled visit; in this instance, Week 2 and Week 4 will be assigned based on the assessment being windowed as Week 4 per the above rule, and then the following windowing based on analysis day (relative to first date of double-blind medication) will be applied:

- Date of diary assessment after scheduled Baseline visit from Analysis Day 6 up to and including Analysis Day 22: Assigned as Week 2;
- Date of diary assessment on or after Analysis Day 23 up to and including the day before the scheduled Week 4 visit: Assigned as Week 4.

For diary data, with the exception of week 12 only the latest 10 complete diary day observations leading up to any scheduled visit will be included in the analysis of the diary. For week 12, the diary within the latest 10 complete diary day observation will be included if available. If not then the complete diary day observation within the latest 14 days will be included. For both scenarios, there must be 4 or more complete diary days available for the period to be analyzed. Otherwise, if there are less than 4 complete diary days available, the period will be set to missing for the analysis.

Visit Windowing for Non-Diary Data:

For any non-diary data involving two scheduled visits (OAB-q-LF, WPAI-US, EQ-5D, Physical Exam and ECG), the analysis visit will be assigned as the scheduled visit performed in the eCRF. For all other non-diary data, analysis visit will be windowed using the rules given in [Table 6.5.1](#) below. These adjusted analysis-defined windows will be

based on the collection schedule listed in the protocol and variables will be windowed to the closest scheduled visit for that variable.

There is no analysis window for the Screening, Run-in, or Baseline visit; those will be analyzed as collected. Post-baseline visits will be windowed based on the target day of the analysis window, which is relative to Day 1 (the first day of double-blind medication).

Table 6.5.1: Analysis Window

Visit Name	Nominal Visit	Target Day	Analysis Window
Screening	Visit 1	-49 to -15	N/A
Run-in	Visit 2	-14	N/A
Baseline	Visit 3	1	N/A
Week 4	Visit 5	29	[2, 42]
Week 8	Visit 6	57	[43, 70]
Week 12	Visit 7	85	[71, 98]
Follow-up	Visit 8	113	[99, ∞)

If a patient has multiple values of the same measure in an analysis window, then the value collected closest to the target day will be used. If the visits are equidistant from the nominal day, then the later visit will be used. All values will be stored in analysis datasets.

A laboratory result based on an inadequate sample will not be used in the presentation of sample statistics if a repeat sample was drawn to replace the sample, but the inadequate sample will be listed.

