6. The Patient Voiding Diary should be completed by the patient on all of the 7 Diary Days **prior to** the Run-in Visit (days -21 to -15), Baseline Visit (days -7 to -1), Week 2 Visit (days 8 to 14), Week 4 Visit (days 22 to 28), Week 8 Visit (days 50 to 56), and Week 12 Visit (days 78 to 84). Patient will receive SMS text alerts and/or phone call reminders to complete the Diary.

7. The Urine Volume collection and Urine Volume Diary completion should be performed by the patient on one (1) of the 7 Diary Days prior to the Run-in, Baseline, and Weeks 2, 4, 8, and 12 Visits.

Diary and Visit Reminders

8. Patient will receive phone call reminders from the site to complete the Diary on approximately the first day and third day of each diary collection period (or next business day). Patient may consent to additional SMS Text reminders (where available).

Patient Reported Outcomes

9. Vital signs, followed by PRO Questionnaires will be the first procedure performed at visits that include PRO administration. Questionnaires will be administered at the site in the order listed in the Schedule of Activities.

Post Void Residual Volume

10. All efforts will be made to ensure the same device and operator are used for all PVR volume measurements for individual patients.

Physical/ECG/Vitals

11. A Complete Physical Exam will be performed at the Screening Visit and will include a digital rectal exam for all males. Focused physical examinations will be performed at the Run-in and Follow-up Visits, which will include a pelvic exam for women only as needed to confirm prolapse.

12. A single 12-lead ECG will be obtained at Screening.

13. Vital Signs includes Blood Pressure (average of three measurements taken 1-2 minutes apart after sitting for 5 minutes), Heart Rate, Temperature, Respiration Rate and Weight. Height will be measured only at Screening.

Adverse Events

14. Adverse events will be collected from the time a patient provides informed consent to participate in the study until the Follow-up Visit is completed.

15. Serious adverse events will be collected from the time a patient provides informed consent to participate in the study until the Follow-up Visit is completed.

Prior and Concomitant Medications

16. Concomitant medications will be reviewed and recorded at each study visit from the Screening through the Week 12 and at any Unscheduled Visits. Medications taken within 1 year of the Screening Visit for the treatment of OAB will also be recorded.

Labs

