OAB Wet: Patients are considered OAB Wet according to the following criteria:

- An average of ≥ 8.0 micturitions per Diary Day; and,
- An average of ≥ 1.0 UUI episodes per Diary Day; and,
- If stress urinary incontinence (SUI) is present, the total number of UUI episodes must be greater than the total number of SUI episodes.

OAB Dry: Patients are considered OAB Dry according to the following criteria:

- An average of ≥ 8.0 micturitions per Diary Day; and,
- An average of ≥ 3.0 urgency episodes per Diary Day; and,
- An average of < 1.0 UUI episodes per Diary Day

OAB-d Type Missing: Patients are considered non-categorized for OAB if neither of the above criteria is achieved.

Where OAB Wet is discussed in this document, it pertains to patients randomized under the strata of OAB Wet; where all OAB Patients are discussed, this relates to all patients randomized as either OAB Wet or OAB Dry. Under the randomization strata, all patients are categorized as OAB Wet or Dry; missing is not present. Unless otherwise stated, for the purposes of the analyses, OAB Type (i.e. as randomized) will be used.

Diary Day

A “Diary Day” is defined as the time between when the patient gets up for the day each morning and the time the patient gets up for the day the next morning as recorded in the patient voiding diary.

Complete Diary Day

A “Complete Diary Day” is defined as a Diary Day that includes input of micturition data by patients on the voiding diary. Unless a patient indicated “No” to the questions of “Did you record each time you urinated or leaked during this Diary Day” the Diary Day is considered complete.

For post-baseline diaries at Weeks 4 and 8, only complete diary days within 10 days prior to the study visit will be included. For the Week 12/Early Termination diary, only complete diary days within 14 days prior to the study visit will be included. For the Week 2 diary, complete diary days within 10 days prior to the target Week 2 day will be used. For diaries at all visits, if a patient has fewer than 4 complete diary days, that will be identified as a significant protocol deviation and that diary data will be excluded from all analysis.

Definition of Baseline for Patient Voiding Diary Endpoints

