Baseline will be the data collected during the Run-in Period. If greater than 10 complete diary days are available in the Run-in diary, only the complete diary days within the 10 days prior to the Baseline visit will be used; if 4 or more and less than 10 complete diary days are available, all complete diary days in the Run-in diary will be used to calculate Baseline. If less than 4 complete diary days are available, the Baseline will be regarded as missing. For a patient to have an evaluable change from baseline, the patient must have both a baseline diary and a post-baseline diary from any post-baseline timepoint, after analysis window has been applied (i.e., Week 2, Week 4, Week 8, or Week 12).

Definition of Baseline for Endpoints not Derived from the Patient Voiding Diary

Baseline value for all secondary efficacy, exploratory and safety endpoints will be defined as the last non-missing assessment before starting double-blind treatment.

Screening/Washout Period

The Screening/Washout Period covers Day -49 (Screening Visit) to Day -15 (the day before the start of the Run-in Period), which includes a 28-day washout period followed by 7-days of Diary completion. Patients not requiring the 28-day washout period can begin the 7-day Diary the day after the Screening Visit.

Run-in Period

The Run-in Period covers the duration between screening (Day -14) and the day before baseline (Day 1). There is no day 0 included in the study.

Treatment Period

The Treatment Period covers the duration that a patient is in the study from Baseline (Day 1) and Week 12.

Safety Follow-up Period

The Safety Follow-up Period continues for 28 days after the last dose of study treatment (Day 85) through Day 113 (Follow-up Visit).

Definition of Study Completion

A patient will be defined as “completed” if she/he completes the Week 12 study visit.

End of Study Definition

End of study is defined as the date when the patient has completed one of the following: completed the follow-up visit after the Week 12 visit, enrolled into the extension trial 3004, permanently discontinued from the study, or lost to follow-up. When lost to follow-up, the latest date of assessment/event in the database will be used as the last known date of the patient in study.

Day of Study Event (Post-Randomization)

Day of study event = Event Date – Date of Randomization (Day 1) + 1.

Day of Study Event (Pre-Randomization)

Day of study event = Event Date – Date of Randomization (Day 1).

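### Section 6.5 makes the Week 2 diary label depend on a performed Week 4 visit, so without that visit a valid early diary can go unlabelled or enter the MMRM as Week 12

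*SAP*

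**What the plan says.** Section 6.5 places diary records that carry only a date or time by visit: "the record will be assigned based on the dates of the scheduled visits performed". It then makes an exception: "This applies for all analysis visits except for Week 2 and Week 4 as there is no Week 2 scheduled visit". For these two time points it sets an order of steps: "Week 2 and Week 4 will be assigned based on the assessment being windowed as Week 4 per the above rule", followed by a split on analysis day. The first branch of the split reads "Date of diary assessment after scheduled Baseline visit from Analysis Day 6 up to and including Analysis Day 22: Assigned as Week 2". The second runs from Day 23 to the day before the Week 4 visit. Nothing is said about a Week 4 visit that was not performed.

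Other parts of the SAP bear on this:
- Section 6.3 (Complete Diary Day): "For the Week 2 diary, complete diary days within 10 days prior to the target Week 2 day will be used". This does not mention the Week 4 visit.
- Section 6.3, same paragraph: "For the Week 12/Early Termination diary, only complete diary days within 14 days prior to the study visit will be included". Weeks 4 and 8 use 10 days, and every diary needs at least 4 complete days.
- Section 6.3 (diary baseline), on what makes a change evaluable: "the patient must have both a baseline diary and a post-baseline diary from any post-baseline timepoint, after analysis window has been applied". Week 2 is listed there, and again at the start of Section 8, as a qualifying time point.
- Section 5.5: FAS and FAS-I membership requires one evaluable change from baseline.
- Section 3.11: Week 2 diary on Days 8 to 14, Week 4 diary on Days 22 to 28. Week 12 and early withdrawal share one visit column, and Week 12 activities are done at withdrawal.
- Section 8.1.1.1: the primary MMRM uses Weeks 2, 4, 8 and 12.

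**The concern.** The rule ties a diary kept at home in the second week to a clinic visit two weeks later. Patients without that visit are mainly early leavers. The MMRM has little post-baseline information on them, and its missing-at-random argument uses what there is. If their Week 2 diary has no label, that information is lost, and with it possibly their place in the FAS. If the diary is labelled Week 12/Early Termination, second-week data count as the primary outcome. That amounts to carrying an early value forward by labelling, in an analysis that Section 6.4 describes as free of imputation and for which LOCF is only a sensitivity analysis. Two programmers, one following Section 6.3 and one following Section 6.5, could also build different analysis sets.

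**Working it through.** **The plan's own figures.** Section 3.8 gives 98% power for each co-primary endpoint and 96% for both. With power = Φ(δ/(σ√(2/n)) − 1.96):
- Micturitions (n = 450 per arm, δ = 0.6, σ = 2.20): Φ(4.09 − 1.96) = 98.3%.
- UUI (n = 337 per arm, δ = 0.51, σ = 1.68): Φ(3.94 − 1.96) = 97.6%.
- Product: 96.0%.

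These reproduce the stated values. The point does not depend on them; they serve below to judge size.

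**Applying the rules to a patient with a full Week 2 diary (Days 8 to 14) and no Week 4 visit.**

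(a) *No later visit.* There is no performed visit to window to, so the diary gets no label. If no other post-baseline diary is labelled, there is no evaluable change from baseline and the patient is outside the FAS and FAS-I.

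(b) *A withdrawal visit on day d comes next.* Records are windowed to Week 12/Early Termination, with a look-back of Days d−14 to d−1. Counting planned diary days inside it:

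| Withdrawal visit day | From Days 8–14 | From Days 22–28 | Total |
|---|---|---|---|
| 15–22 | 7 | 0 | 7 |
| 23 | 6 | 1 | 7 |
| 24 | 5 | 2 | 7 |
| 25 | 4 | 3 | 7 |
| 26 | 3 | 4 | 7 |
| 27 | 2 | 5 | 7 |
| 28 | 1 | 6 | 7 |

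For example, d = 26 looks back over Days 12 to 25, which hold Days 12–14 (3) and Days 22–25 (4). A patient who kept the planned diaries therefore has 7 days against a minimum of 4. That patient stays in the FAS, with data from Days 8 to 27 at most, labelled Week 12. By contrast, Table 6.5.1 puts windowed non-diary data from a withdrawal visit on these days in Week 4 (Days 2 to 42).

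(c) *Week 4 skipped, Week 8 attended on Day 57.* Under the calendar rule of Section 6.3 (Days 47 to 56), no Week 2 day is used. Under Section 6.5, the latest 10 complete diary days are Days 50–56 (7 days) plus 3 earlier ones. Those are Days 26–28 if a Week 4 diary was kept and Days 12–14 if not. Either way the Week 2 value is missing, but the Week 8 diary keeps the patient in the FAS.

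**The two Week 2 windows.** Section 6.3 counts 10 days back from target Day 15, so about Days 5 to 14. Section 6.5 uses Days 6 to 22.

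**Size.** Section 3.8 assumes 10% discontinuation: 0.10 × 1,400 = 140 patients. It gives no timing, so the share leaving on Days 15 to 28 is an assumption:
- 5%: 140 × 0.05 = 7
- uniform over 84 days: 140 × 14/84 = 23.3
- 30%: 140 × 0.30 = 42

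For vibegron and placebo alone (1,000 patients, 100 discontinuers) the same shares give 5, 16.7 and 30. A 3% loss of evaluable patients would leave power at 98.1% and 97.3%.

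**The case against.** Several objections carry weight.

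- *FAS loss is narrow.* A reader might infer that anyone whose withdrawal visit falls on Day 26 or later drops out, because at most 3 of Days 8–14 remain in the look-back. The documents do not support this: the Week 4 diary is also scheduled, and the table shows 7 planned days for every visit from Day 15 to Day 28. FAS loss needs a patient with no later visit, or gaps in the diary. Since Section 3.11 asks for Week 12 activities at withdrawal, the first group is essentially those truly lost to follow-up. This objection stands.
- *The counts are not exclusions.* The 7 to 42 are patients exposed to the rule, over three arms and under assumed timing. A difference between arms is possible, but nothing in the SAP shows one, and the rule is the same for all arms. This also stands.
- *Section 6.3 may rescue the diary.* It is tempting to say that it states the opposite of Section 6.5. More exactly, it selects days within a Week 2 diary by target day and does not say that it replaces the assignment step. A reader who joins the two sections could keep the diary; a reader of Section 6.5 alone could not. The ambiguity remains.
- *The visit-date rule covers only records with a date or time.* Assessments tied to a visit go to the visit entered. But Section 6.5 itself says that Week 2 has no scheduled visit, so the SAP offers no such route for Week 2.

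**Conclusion.** The point holds as a defect in the windowing rule. Followed literally, Section 6.5 leaves a valid Week 2 diary unlabelled, places it at Week 12/Early Termination or merges it into Week 8 whenever no Week 4 visit was performed. This does not fit Section 6.3 or the use of Week 2 as a qualifying time point. The more serious likely effect is mistiming at the primary time point; removal from the FAS or FAS-I is a narrower risk. The number affected is unknown: 7 to 42 exposed patients under the assumed 5% to 30%, plus any who merely skip Week 4, with only some of the exposed losing FAS membership. The effect on power is negligible. No bias in the treatment difference has been shown or quantified, and the documents would not support a claim that the co-primary results are materially distorted. It should be corrected before unblinding because the written rule governs the primary model's input and the correction is simple.

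**What to change.** In Section 6.5:
1. Assign every diary record on Analysis Days 6 to 22 to Week 2 by analysis day alone, whether or not a Week 4 visit was performed and whichever visit follows.
2. Apply the visit-based rule only to the remaining records.
3. State an analysis-day rule for Week 4 diary days from Day 23 when no Week 4 visit was performed, so that they are not labelled Week 12. The Week 4 upper limit of Day 42 in Table 6.5.1 is one limit that the SAP already uses for non-diary data.

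In Section 6.3, refer to this same Day 6 to 22 window for Week 2.

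All seven of Days 8 to 14 then become Week 2 in each case above, and a patient with a baseline diary keeps an evaluable change from baseline. Day 22, the first planned day of the Week 4 diary, falls in the Week 2 window under the present text too; the change does not alter that. The cost is a few sentences and a few lines of programming before unblinding, with no new data. If the programmers already work this way, only the text needs to change.

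### For date-stamped diary records, the fixed Day 22/23 cut in SAP 6.5 conflicts with the SAP's own Week 4 diary schedule and with the 6.3 look-back rule, and the SAP does not say which governs

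*SAP*

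**What the plan says.** **Schedule (SAP 3.11).** Table 3.11.1 sets the Week 4 visit at Day 29 with a window of 3 days either side. Footnote 6 asks for the voiding diary on the 7 Diary Days before each visit, which on target is "Week 4 Visit (days 22 to 28").

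**Assignment (SAP 6.5).** A diary assessment performed at a specific visit is analysed at the visit entered. Records with only a date/time are assigned by date. Because Week 2 has no clinic visit, the interval between Baseline and the Week 4 visit is split at a fixed day. Records "from Analysis Day 6 up to and including Analysis Day 22: Assigned as Week 2", and records "on or after Analysis Day 23 up to and including the day before the scheduled Week 4 visit: Assigned as Week 4". In addition, "only the latest 10 complete diary day observations leading up to any scheduled visit will be included" (Week 12 is excepted), and "there must be 4 or more complete diary days available for the period to be analyzed"; otherwise the period is set to missing.

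**Look-back (SAP 6.3, Complete Diary Day).** "For post-baseline diaries at Weeks 4 and 8, only complete diary days within 10 days prior to the study visit will be included". Week 2 has its own look-back of 10 days, counted from its target day because there is no visit. Neither rule mentions Day 22 or Day 23.

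**Use (SAP 8.1.1.1 and 8.1.2.1).** Weeks 2, 4, 8 and 12 all enter the primary MMRM for both co-primary endpoints, and the Week 2, 4 and 8 estimates are tabulated.

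**The concern.** Day 22 is the midpoint between target Days 15 and 29. A midpoint cut suits a measurement taken at the visit itself. Diary days come 1 to 7 days before the visit, so the same cut can fall inside the Week 4 diary, and it does so whenever the visit is on target or early. Days recorded exactly as the schedule asks are then relabelled or lost, and some compliant patients have no Week 4 value.

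Section 6.3 gives a second rule for the same visits, and nothing in the SAP ranks the two. Two programmers could follow the text faithfully and produce different Week 2 and Week 4 values for both co-primary endpoints.

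**Working it through.** **Inputs.** Week 4 target Day 29 ± 3, so visit day v = 26 to 32 (Table 3.11.1). Diary on Days v − 7 to v − 1 (footnote 6). Analysis Day is counted from the first double-blind dose (6.5), which is witnessed at the Baseline Visit (footnote 22), so Analysis Day equals Study Day. Cut at Day 22/23 and minimum of 4 complete days (6.5). Look-back limits from 6.3.

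**Reproducing the schedule.** Visit day minus 7 to visit day minus 1 gives Days 8–14 for target Day 15, 22–28 for Day 29, 50–56 for Day 57 and 78–84 for Day 85. These match footnote 6.

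**Applying 6.5 to a full 7-day diary.** Days kept for Week 4 = number of days from max(23, v − 7) to v − 1. Days labelled Week 2 = 7 minus that number.

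| Visit day | Diary days | Kept for Week 4 | Labelled Week 2 | 6.3 rule alone, Week 4 |
|---|---|---|---|---|
| 26 | 19–25 | 3 (missing) | 4 | 7 |
| 27 | 20–26 | 4 | 3 | 7 |
| 28 | 21–27 | 5 | 2 | 7 |
| 29 | 22–28 | 6 | 1 | 7 |
| 30 | 23–29 | 7 | 0 | 7 |
| 31 | 24–30 | 7 | 0 | 7 |
| 32 | 25–31 | 7 | 0 | 7 |

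- For a Day 26 visit only Days 23, 24 and 25 lie between the cut and the visit, so no dated diary can reach 4 days under 6.5.
- For a Day 27 visit exactly 4 days remain, so one incomplete day loses Week 4. If each day is complete independently with probability p, the loss is 1 − p⁴: 34.4% at p = 0.90 and 7.8% at p = 0.98. These values of p are assumptions; the SAP gives none.
- The latest-10 limit does not bind for Week 4. Even for a Day 32 visit there are only 9 calendar days from Day 23 to Day 31.

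**How 6.3 changes this.**

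1. *6.3 as a limit applied after 6.5.* Days v − 10 to v − 1 contain the whole diary, so the limit removes nothing more and restores nothing: Week 4 stays at 3, 4, 5, 6, 7, 7, 7. The 6.3 Week 2 limit covers Days 5 to 14 (10 days before Day 15), so the displaced 4, 3, 2 and 1 days (visits on Days 26 to 29) are used at no visit.
2. *6.5 without the 6.3 Week 2 limit.* The displaced days join a complete Week 2 diary on Days 8–14. They make up 4 of 11, 3 of 10, 2 of 9 and 1 of 8 Week 2 days. If the latest-10 limit also applies at Week 2, the first share is 4 of 10.
3. *6.3 as a stand-alone rule.* All 7 days are kept for every permitted visit, and the 6.5 split has no function for Week 4.

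**Checking the proposed start.** Start of Week 4 = min(23, v − 7) = 19, 20, 21, 22, 23, 23, 23 for v = 26 to 32. It keeps 7 days in every case, leaves Days 8–14 in Week 2, and changes nothing for visits on Days 30 to 32.

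**The case against.** The strongest reply is that no data need be lost. Section 6.3 gives a Week 4 rule with no Day 23 floor, and read alone it keeps the whole diary. Section 6.5 also lets an assessment tied to an entered visit follow that visit, and the SAP does not say which eDiary records carry a visit label. Both points stand, and they limit the claim to 6.5 as written for records with only a date/time. They do not remove the conflict: if 6.3 governs, the Day 22/23 split in 6.5 contradicts it.

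A reader might infer that 6.3 settles the order, because it requires "a post-baseline diary from any post-baseline timepoint, after analysis window has been applied". That phrase belongs to the definition of an evaluable change from baseline. It does not rank the look-back against the assignment. Applying 6.3 as a later limit would also make much of the 6.5 Week 2 range idle, since Days 15 to 22 could never count.

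Materiality is also fairly challenged. Only one of the seven permitted visit days loses Week 4 with a full diary, Week 4 is an intermediate visit, and a patient with other post-baseline diaries stays in the MMRM. This stands and keeps the point at the level of a needed correction to the text.

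**Conclusion.** The point holds for date-stamped diary records. Under 6.5 as written, a patient with a permitted Day 26 visit and a complete diary has no Week 4 value, Day 27 leaves no spare day, and even an on-target visit loses a scheduled diary day. Under the alternative reading nothing is lost at Week 4, but two sections of the SAP then disagree and neither is given priority. Either way the text must be reconciled.

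Two stronger readings go too far. One is that early Week 4 visits are lost whichever rule applies; 6.3 read alone keeps them. The other is that the primary Week 12 comparison is distorted. The cut does not reassign Week 12 diary days, and nothing in the SAP points to a difference by treatment arm. The effect is on the Week 4 and Week 2 estimates, and on Week 12 only through the repeated-measures model. The SAP does not give the spread of visit days, so no number of patients can be stated.

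The counts assume that the diary occupies the 7 days before the actual visit and that the first double-blind dose is taken at Baseline.

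**What to change.** In 6.5, start Week 4 at the earlier of Analysis Day 23 and 7 days before the actual Week 4 visit, and end Week 2 on the day before that start. In both 6.3 and 6.5, state how the 6.3 look-back limits combine with the 6.5 assignment for Weeks 2 and 4, whether the latest-10 limit applies to Week 2, and whether Week 2 diary days after Day 14 count.

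Downside: for early Week 4 visits, a few days of a late Week 2 diary would be labelled Week 4. For example, with a Day 26 visit, a Week 2 diary kept on Days 16–22 would retain 3 days in Week 2 instead of the 7 that 6.5 alone now gives. The 6.3 Week 2 limit, if it applies, already excludes all 7. A fixed earlier cut would impose this on every patient, so the visit-anchored start is preferable.

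The cost is wording in two sections and a small programming change before unblinding. Data collection is unaffected.

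A minor separate item is the Week 12 look-back. Section 6.3 uses all complete days within 14 days before the visit; 6.5 uses the latest 10 complete-day observations, with 14 days as a fallback. With complete days at 1–7 and 11–14 days before the visit, the first uses 11 and the second 10. One rule should be stated in both places.
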